## 7. SAFETY ANALYSIS

Safety assessments will include assessment of AEs, chemistry, hematology (complete blood count and differential), COVID-19 clinical features, vital signs, and hospital interventions. All safety summaries (or analyses if applicable) will be conducted using the SAF population. No formal hypothesis testing will be performed to compare differences between treatment groups.

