8.3.8 Adverse Event Documentation

All AEs and SAEs occurring on Day 1 through the Day 29 (± 1 day)/Final Visit must be fully recorded in the subject’s medical record and CRF, and SAE form (if serious).

At the time of the Day 60 (± 2 days) and Day 90 (± 2 days) Phone Checks any additional SAEs/non-serious AEs will also be collected and recorded.

It is the responsibility of the investigator to ensure that AEs are appropriately recorded.

AEs will be collected through directly observed events or spontaneously volunteered by the subject. Clearly related signs, symptoms and abnormal diagnostic procedures should preferably be grouped together and recorded as a single diagnosis or syndrome wherever possible.

The following variables must be recorded:

- The verbatim term (a diagnosis is preferred)
- Date/time of onset
- Date/time of resolution
- Severity (mild, moderate, severe [Grade 3 to Grade 5])
- Causality (unrelated, possibly related, definitely related)*
- Seriousness (yes, no)
- Action taken (with regard to IP)
- Other action (to treat the event)
- Outcome and sequel (follow-up on AE)

*Causality assessment will be made only when the AE occurs after the subject has initiated at least one infusion of the IP. An AE occurring before subject’s exposure to IP will be always labeled as “unrelated”.

GRIFOLS Bioscience Industrial Group	Number	BlG-CL-PRT-000020	Version	4.0	Status	Effective	Effective Date	19-Jul-2021	Page	61 of 91
	GC2007 - A Multicenter, Randomized, Open-label Parallel Group Pilot Study to Evaluate Safety and Efficacy of High Dose Intravenous Immune Globulin (IVIG) plus Standard Medical Treatment (SMT) versus SMT alone in									

For AEs that occur during infusions, the infusion rate in effect at the time of onset of the AE, the time of onset of the AE and the time of AE change materially in intensity and/or resolve will be captured.

In addition to the investigator's own description of the AE, each AE will be encoded according to the Medical Dictionary for Regulatory Activities (MedDRA).

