#### 2.1.4 Safety Objective

To determine the safety and tolerability profile through Day 29 of high dose IVIG plus SMT versus SMT alone in hospitalized subjects with COVID-19.

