## 7.2.5 Adverse Event Summaries

All AEs (serious and non-serious) occurring after randomization and before the end of study, regardless of relationship to IP, will be included and classified by SOC and PT using MedDRA.

For TEAEs, the following will be summarized and presented for the SAF population:

- i. An overall summary of TEAEs, which includes:
  - a. the number and percentage of subjects experiencing a TEAE
  - b. the number and percentage of subjects experiencing a TEAE by strongest relationship to IP
  - c. the number and percentage of subjects experiencing a TEAE by greatest severity
  - d. the number and percentage of subjects experiencing a TEAE with Grade  $\geq 3$
  - e. the number and percentage of subjects experiencing a treatment-emergent SAE
  - f. the number and percentage of subjects experiencing a TEAE leading to death
  - g. the number and percentage of subjects experiencing a TEAE leading to study withdrawal
- ii. the number and percentage of subjects experiencing a TEAE by SOC and PT.
- iii. the number and percentage of subjects experiencing an adverse drug reaction (ADR; i.e., potentially related TEAE) by SOC and PT, where an ADR is defined as any TEAE with a causal relationship to IP assessed as 'Possibly Related' or 'Definitely Related'.
- iv. the number and percentage of subjects experiencing a TEAE by SOC, PT and the strongest relationship to IP
- v. the number and percentage of subjects experiencing a TEAE by SOC, PT and the greatest severity
- vi. the number and percentage of subjects experiencing a TEAE with Grade  $\geq 3$  by SOC and PT
- vii. the number and percentage of subjects experiencing an ADR with Grade  $\geq 3$  by SOC and PT
- viii. the number and percentage of subjects experiencing a treatment-emergent SAE by SOC and PT
- ix. the number and percentage of subjects experiencing a potentially related treatment-

- emergent SAE by SOC and PT
- x. the number and percentage of subjects experiencing a TEAE leading to death by SOC and PT
- xi. the number and percentage of subjects experiencing a TEAE leading to study withdrawal by SOC and PT

In the overall summary of TEAEs table (i), besides tabulating the number and percentage of subjects, the total number of TEAE episodes will also be provided. If a subject has repeated episodes of a particular TEAE, all episodes will be counted in the summary table.

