In the remaining summary tables, the incidence of TEAEs will be calculated by dividing the number of subjects who have experienced the event by the total number of subjects. Thus, the incidence of TEAEs is shown in terms of the total number of subjects and not in terms of the total number of episodes. If a subject has repeated episodes of a particular TEAE, only the most severe episode, or the episode with the strongest causal relationship to IP, will be counted in the summary tables.

A subject with more than one type of TEAE in a particular SOC or PT will be counted only once in the total of subjects experiencing TEAEs in that particular SOC or PT.

All occurrences of all AEs and SAEs will be listed for each subject, grouped by treatment group. The listing will contain the following information: treatment group, verbatim term, SOC, PT, severity (mild, moderate, severe [Grade 3-5]), grade, relationship to IP if applicable, date/time and day of onset, date/time and day of resolution, action taken with regard to IP, whether additional non-drug treatment was given to treat the adverse event, the outcome, whether the event was an SAE, whether it led to study withdrawal, whether it occurred during IP infusion, and whether it is a TEAE. Listings will be sorted by treatment group, subject identification number, onset date, SOC, and PT. If the onset date is completely missing, then these events will be presented first. If the onset date is missing a month or a day, then these events will be presented before any complete dates.

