### **8. INTERIM ANALYSES**

An interim analysis will be conducted after 50 subjects (approximately 25 per group) for safety variables through Day 29. Due to the exploratory nature of this phase 2 study, the multiplicity adjustments will not be considered. This interim evaluation simply represents Sponsor safety due diligence. This interim analysis will analyze safety variables including, but not limited to, the following: adverse events (see Section 7.2), clinical laboratory parameters (see Section 7.3), and vital signs (see Section 7.4). The relevant methods described in Section 7 (Safety Analysis) of this SAP intended for the final analysis will also be applicable to the interim analysis.

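### The safety objective compares the arms, but adverse-event endpoints are reported only as per-arm counts and percentages; a descriptive risk difference with a 95% interval should be added

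*SAP*

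**What the plan says.** The objective in SAP 2.1.4 (and Protocol 3.2) is comparative: "To determine the safety and tolerability profile through Day 29 of high dose IVIG plus SMT versus SMT alone". SAP 2.2.4 sets three families of endpoint, all cumulative incidences: treatment-emergent SAEs to the Day 90 phone check, Grade 3-5 TEAEs to Day 29, and all TEAEs to Day 29. Each has a potentially related counterpart.

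The planned output in SAP 7.2.5 is a list of tables of one form, for example "the number and percentage of subjects experiencing a treatment-emergent SAE by SOC and PT". Incidence is a crude proportion: "the incidence of TEAEs will be calculated by dividing the number of subjects who have experienced the event by the total number of subjects". The overall table adds episode counts. No item in the list is a difference, a ratio or an interval, and Protocol 9.1 adds none. SAP 7 states "No formal hypothesis testing will be performed to compare differences between treatment groups".

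SAP 8 says "An interim analysis will be conducted after 50 subjects (approximately 25 per group) for safety variables through Day 29", and then "The relevant methods described in Section 7 (Safety Analysis) of this SAP intended for the final analysis will also be applicable to the interim analysis".

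Two other places bear on the point. SAP 6.1 gives Day 29 mortality a between-arm risk difference with an exact unconditional 95% interval. On relatedness, Protocol 8.3.8 says "Causality assessment will be made only when the AE occurs after the subject has initiated at least one infusion of the IP".

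**The concern.** A comparative objective calls for a comparative estimate. With two percentages side by side and nothing else, a reader at the interim or the end must judge by eye whether the IVIG arm shows an excess, and the report never says how large an excess the data leave possible. At 25 or 50 per arm that remaining range is wide. Similar percentages are weak evidence of no added harm, and nothing in the tables says so.

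The potentially related half of each endpoint cannot fill the gap. Causality is judged only after an infusion, so a subject never given Gamunex-C contributes zero by rule. The SMT-alone column in those tables is empty by construction and carries no comparative information.

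**Working it through.** **Inputs from the documents.** 1:1 allocation (SAP 3.2.1); about 100 subjects, so about 50 per arm (SAP 9); about 25 per arm at the interim (SAP 8); two-sided 5% level, hence 95% intervals (SAP 4). No adverse-event rate, margin or power is stated, so there is no figure in the plan to reproduce. All event counts below are assumptions.

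**Step 1: interval for the difference when both arms show the same count.** With p = x/n and z = 1.96, the Wilson limits l and u for one arm are

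[p + z²/2n ± z√(p(1−p)/n + z²/4n²)] / (1 + z²/n).

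Newcombe's limits for a zero observed difference are ±√[(u − p)² + (p − l)²].

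For 5/50 in each arm, l = 0.0435 and u = 0.2136. The half-width is √[(0.2136 − 0.1000)² + (0.1000 − 0.0435)²] = √(0.01290 + 0.00319) = 0.127, or ±12.7 points. Equal counts with equal n must give an interval symmetric about zero, which is a useful check on any software used.

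**Step 2: upper limit for the risk ratio.** With equal counts the ratio is 1, and the log-method upper limit is exp[1.96 √(2(1/x − 1/n))]. For 5/50: √(2(0.20 − 0.02)) = 0.60, and exp(1.176) = 3.24. A score interval was computed as a cross-check.

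| Per arm | Count in each arm | % | Difference, 95% limits (points) | Ratio upper limit, log | Ratio upper limit, score |
|---|---|---|---|---|---|
| 50 | 5 | 10 | ±12.7 | 3.24 | 3.06 |
| 50 | 12 | 24 | ±16.6 | 2.01 | 1.99 |
| 50 | 15 | 30 | ±17.5 | 1.82 | 1.81 |
| 50 | 25 | 50 | ±18.9 | 1.48 | 1.49 |
| 25 | 5 | 20 | ±22.1 | 3.03 | 2.90 |
| 25 | 9 | 36 | ±25.1 | 2.09 | 2.09 |
| 25 | 10 | 40 | ±25.4 | 1.97 | 1.97 |

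**Step 3: when is a doubling still possible?** On the ratio scale, with equal percentages, 2 lies inside the interval up to about 24% per arm at 50 (12/50 sits on the boundary) and up to 36% at 25 (9/25). Above those rates equal percentages exclude a doubling, as at 15/50 and 10/25.

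The scale matters. If the limit for the difference is instead read against the observed SMT percentage, the cut-offs are lower: 14% at 50 per arm (7/50, limit +14.1; at 8/50 the limit is +14.7 against 16) and 20% at 25 (5/25, limit +22.1; at 6/25 it is +23.1 against 24).

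**Step 4: similar but unequal percentages.** At 18/50 versus 15/50 (36% versus 30%) the ratio is 1.2. The standard error of its log is √(1/18 − 1/50 + 1/15 − 1/50) = 0.287, and the upper limit is about 2.1. At 12/25 versus 10/25 (48% versus 40%) the upper limit is about 2.25. A small observed excess therefore keeps a doubling in play at higher rates than in Step 3.

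**The case against.** Descriptive adverse-event tables are a defensible convention in a pilot, and the per-arm counts let any reader compute a difference and its interval afterwards. That is fair: nothing is lost for good, and this is an improvement in reporting, not a flaw that invalidates the trial. It does not remove the point, because the interim is the sponsor's own safety review and the uncertainty should be in front of those who read it.

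Several stronger readings are tempting but not supported:

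- A reader might infer that at these sample sizes a doubling of harm is never excluded. That depends on the event rate, which the documents do not give. Nothing shows that the three aggregate endpoints in ICU patients fall below the cut-offs in Step 3.
- A reader might infer that the SAP forbids intervals. The sentence in SAP 7 rules out tests only; the absence of intervals comes from the list in 7.2.5.
- A reader might infer that the sponsor will declare safety because two percentages look alike. No section sets such a rule. The interim does not interrupt the study, and suspension of enrolment rests on the event-count criteria and committee review in Protocol 8.5. The risk is one of interpretation.
- A reader might treat low power to detect harm as the defect. Low power follows from the size of the trial, and an added interval does not change it.
- A reader might think no harm is compared between arms. Day 29 mortality is, with an interval.

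One objection changes the fix. Under Protocol 4.1.4 and 8.3.3.1, COVID-19 symptoms are not recorded as TEAEs unless a causal link to IVIG is suspected. That exception cannot arise in subjects given SMT alone, and the trial is open-label. Recording can therefore differ by arm, and an interval reflects sampling error only.

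**Conclusion.** The point stands as a low-cost improvement. The plan states a comparative safety objective but gives no between-arm estimate or interval for any adverse-event endpoint at the interim or the final analysis, although it already plans that kind of estimate for mortality. For assumed equal observed counts, the uncertainty left unstated is about ±13 points at 5/50, ±18 at 15/50 and ±25 at 10/25 per arm. The statement about doubling holds only conditionally, within the rate limits in Step 3. Even where a doubling is excluded, a sizeable absolute excess is not: at 25/50 in each arm the ratio limit is about 1.5, but a difference of nearly 19 points remains possible. These figures assume full arms of 25 and 50 and rest on assumed rates.

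**What to change.** In SAP 7.2.5 and SAP 8:

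1. For treatment-emergent SAEs (to Day 90), Grade 3-5 TEAEs (to Day 29) and all TEAEs (to Day 29), add the risk difference, IVIG plus SMT minus SMT alone, with a two-sided 95% interval. Label it descriptive, give no p-value, and name the method (for example Newcombe, or the exact unconditional method already used in SAP 6.1).
2. Require any statement of no excess to quote the upper limit.
3. Beside the TEAE intervals, note that they reflect sampling error only, because COVID-19 symptoms are recorded as TEAEs only when a link to IVIG is suspected and the trial is open-label.
4. Show the potentially related tables for the Gamunex-C arm only, with SMT alone marked not applicable instead of 0%.

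The cost is SAP wording and one extra column in three tables, with no new data or visits. The intervals will be wide, so the safety statement will read less favourably.

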### 7.1 Extent of Exposure and Compliance

The number of doses received, duration of infusion in minutes, infusion rate, the occurrence of dose interruption, whether 100% of study drug infused, total volume prepared, and total volume infused will be summarized for the Gamunex-C plus SMT group. In addition, treatment compliance will be calculated and summarized for this treatment group. The summaries will include descriptive statistics of the treatment compliance as well as number and percentage of subjects with compliance between 80% and 120%.

Treatment compliance (%) will be calculated as follows:

$$\frac{\text{(Total volume infused over all infusions [mL])}}{\text{(Total volume prepared over all infusions [mL])}} \times 100.$$

### 7.2 Adverse Events

All AEs and serious AEs (SAEs) occurring on Day 1 through the Day 29 ( $\pm 1$  day)/Final Visit must be fully recorded in the subject's medical record and eCRF, and SAE form (if serious). At the time of the Day 60 ( $\pm 2$  days) and Day 90 ( $\pm 2$  days) Phone Checks any additional SAEs/non-serious AEs will also be collected and recorded. AEs will be classified by SOC and PT using the most recent version of MedDRA.

#### 7.2.1 Treatment-emergent Adverse Events

For summary purposes, AEs will be classified as treatment-emergent AEs (TEAEs) or non-treatment-emergent AEs (non-TEAEs) depending on the comparison of AE onset date/time with the date of randomization. A TEAE will be defined as an AE which occurred on or after the date of randomization. For adverse events with incomplete start dates/times, the same imputation algorithm for missing or partial date/time information as described in Section 5.6 will be used for the determination of an AE being treatment emergent or not. Briefly, the unknown portions of an AE onset date/time will be imputed to the latest possible before being compared to the date of randomization.

Non-TEAEs will be summarized separately from TEAEs by SOC and PT for each treatment group and overall.

## 7.2.2 Adverse Event Severity

Refer to the study protocol, Section 8.3.5.

## 7.2.3 Adverse Event Relationship to IP

Refer to the study protocol, Section 8.3.4.

## 7.2.4 Serious Adverse Events

Refer to the study protocol, Section 8.3.7.

## 7.2.5 Adverse Event Summaries

All AEs (serious and non-serious) occurring after randomization and before the end of study, regardless of relationship to IP, will be included and classified by SOC and PT using MedDRA.

For TEAEs, the following will be summarized and presented for the SAF population:

- i. An overall summary of TEAEs, which includes:
  - a. the number and percentage of subjects experiencing a TEAE
  - b. the number and percentage of subjects experiencing a TEAE by strongest relationship to IP
  - c. the number and percentage of subjects experiencing a TEAE by greatest severity
  - d. the number and percentage of subjects experiencing a TEAE with Grade  $\geq 3$
  - e. the number and percentage of subjects experiencing a treatment-emergent SAE
  - f. the number and percentage of subjects experiencing a TEAE leading to death
  - g. the number and percentage of subjects experiencing a TEAE leading to study withdrawal
- ii. the number and percentage of subjects experiencing a TEAE by SOC and PT.
- iii. the number and percentage of subjects experiencing an adverse drug reaction (ADR; i.e., potentially related TEAE) by SOC and PT, where an ADR is defined as any TEAE with a causal relationship to IP assessed as 'Possibly Related' or 'Definitely Related'.
- iv. the number and percentage of subjects experiencing a TEAE by SOC, PT and the strongest relationship to IP
- v. the number and percentage of subjects experiencing a TEAE by SOC, PT and the greatest severity
- vi. the number and percentage of subjects experiencing a TEAE with Grade  $\geq 3$  by SOC and PT
- vii. the number and percentage of subjects experiencing an ADR with Grade  $\geq 3$  by SOC and PT
- viii. the number and percentage of subjects experiencing a treatment-emergent SAE by SOC and PT
- ix. the number and percentage of subjects experiencing a potentially related treatment-

- emergent SAE by SOC and PT
- x. the number and percentage of subjects experiencing a TEAE leading to death by SOC and PT
- xi. the number and percentage of subjects experiencing a TEAE leading to study withdrawal by SOC and PT

In the overall summary of TEAEs table (i), besides tabulating the number and percentage of subjects, the total number of TEAE episodes will also be provided. If a subject has repeated episodes of a particular TEAE, all episodes will be counted in the summary table.

In the remaining summary tables, the incidence of TEAEs will be calculated by dividing the number of subjects who have experienced the event by the total number of subjects. Thus, the incidence of TEAEs is shown in terms of the total number of subjects and not in terms of the total number of episodes. If a subject has repeated episodes of a particular TEAE, only the most severe episode, or the episode with the strongest causal relationship to IP, will be counted in the summary tables.

A subject with more than one type of TEAE in a particular SOC or PT will be counted only once in the total of subjects experiencing TEAEs in that particular SOC or PT.

All occurrences of all AEs and SAEs will be listed for each subject, grouped by treatment group. The listing will contain the following information: treatment group, verbatim term, SOC, PT, severity (mild, moderate, severe [Grade 3-5]), grade, relationship to IP if applicable, date/time and day of onset, date/time and day of resolution, action taken with regard to IP, whether additional non-drug treatment was given to treat the adverse event, the outcome, whether the event was an SAE, whether it led to study withdrawal, whether it occurred during IP infusion, and whether it is a TEAE. Listings will be sorted by treatment group, subject identification number, onset date, SOC, and PT. If the onset date is completely missing, then these events will be presented first. If the onset date is missing a month or a day, then these events will be presented before any complete dates.

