### **2.2.4 Safety Endpoints**

The safety endpoints include:

- Cumulative incidence of treatment-emergent serious adverse events (SAEs) and potentially related SAEs through Day 90 Phone Check
- Cumulative incidence of Grade 3-5 treatment-emergent adverse events (TEAEs) and potentially related severe TEAEs through Day 29 as defined in the Common terminology Criteria for Adverse Events (CTCAE), US Department of Health and Human Services, National Institutes of Health (NIH), and National Cancer Institute (NCI)
- Cumulative incidence of all TEAEs and potentially related TEAEs through Day 29

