All subjects will be followed daily through Day 10. After Day 10, if subjects are discharged from the hospital, evaluations at Day 15 and 29 are required. Berlin criteria for ARDS and SOFA score will be assessed on Day 1, 5, 15, and 29. Subjects remaining hospitalized will be followed daily through Day 29. Phone Checks will occur at Day 60 and Day 90 for vital status (living or deceased), any hospital re-admissions or serious/non-serious AEs after the Day 29 Final Clinic Visit. See Appendix A for the Schedule of Events.

Clinical trial finalization will coincide with the last study visit of the last subject enrolled in the clinical trial. For an individual subject, end of study for the purposes of determining disposition and successful study completion is the Day 29/Final Clinic Visit performed at the scheduled on-study timeframe.

An overview of the study design is presented below:

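### SAP 7.2.5 gives all adverse-event tables one undefined end date, which cannot deliver both the Day 29 TEAE endpoints and the Day 90 SAE endpoint

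*SAP*

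**What the plan says.** **Endpoints.** SAP 2.2.4, matching protocol 4.1.4 and 8.1, lists three safety endpoints over two periods:

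- The SAE endpoint has the longer period: "Cumulative incidence of treatment-emergent serious adverse events (SAEs) and potentially related SAEs through Day 90 Phone Check".
- The endpoint for severe events, graded by CTCAE, has the shorter one: "Cumulative incidence of Grade 3-5 treatment-emergent adverse events (TEAEs) and potentially related severe TEAEs through Day 29".
- The endpoint for events of any grade shares that shorter period: "Cumulative incidence of all TEAEs and potentially related TEAEs through Day 29".

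**Tables.** SAP 7.2.5 introduces tables i to xi with one rule: "All AEs (serious and non-serious) occurring after randomization and before the end of study, regardless of relationship to IP, will be included". No table in that list carries a day cut-off. SAP 7.2.1 gives only a lower bound: "A TEAE will be defined as an AE which occurred on or after the date of randomization".

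**End of study.** SAP 3.1 has two statements that could supply the missing date. For the trial, "Clinical trial finalization will coincide with the last study visit of the last subject enrolled in the clinical trial". For one subject, "end of study for the purposes of determining disposition and successful study completion is the Day 29/Final Clinic Visit".

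**Collection.** SAP 7.2 gathers events of both kinds after Day 29. At the Day 60 and Day 90 "Phone Checks any additional SAEs/non-serious AEs will also be collected and recorded".

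**The concern.** The section that specifies the tables states one period for serious and non-serious events, while the section that defines the endpoints states two. Because both kinds of event are collected to Day 90, the choice of end date changes what the tables count.

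At stake is whether the tables report the safety endpoints that the trial named. SAP 7 plans no formal comparison of safety between arms, so these incidence tables are themselves the safety result. A programmer following 7.2.5 literally would produce at least one table that does not match its endpoint, and a reader of the report could not tell which one without knowing the date used.

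**Working it through.** The plan gives no figure to reproduce, so the check is one of consistency.

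**Inputs.** Endpoint periods from SAP 2.2.4; the table rule and table list from SAP 7.2.5; the TEAE definition from SAP 7.2.1; the two end-of-study statements from SAP 3.1; collection after Day 29 from SAP 7.2.

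**Step 1: try each meaning of end of study against each group of tables.**

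| Tables in SAP 7.2.5 | Period in SAP 2.2.4 | End of study = Day 29 | End of study includes the Day 90 contact |
|---|---|---|---|
| All TEAEs and ADRs (i.a-c, ii-v) | Day 29 | Matches | Adds Days 30-90 |
| Grade 3 or higher (i.d, vi, vii) | Day 29 | Matches | Adds Days 30-90 |
| SAEs and related SAEs (i.e, viii, ix) | Day 90 | Omits Days 30-90 | Matches |
| Leading to death or withdrawal (i.f, i.g, x, xi) | None listed | Period unstated | Period unstated |

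The Day 29 meaning fails one of the three endpoints and the Day 90 meaning fails two. No single date satisfies all three.

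**Step 2: which reading is more natural?** The Day 29 statement in SAP 3.1 is limited to disposition and completion. The AE section itself takes in the phone-check events, the TEAE definition has no upper limit, and trial finalization is tied to the last visit of the last subject. These favour the reading that includes Day 90. The safety objective in SAP 2.1.4 does stop at Day 29, which leaves some room for the other reading. The result of Step 1 does not depend on the choice.

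**Step 3: look for a cut-off elsewhere.** SAP 8 limits safety variables to Day 29, but only for the interim analysis. SAP 4.3 summarizes data by nominal visit and gives no AE end date.

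**Step 4: size.** The disputed period is 90 - 29 = 61 days, or 61/90 = 68% of the 90 days. That is a share of time, not of events. The documents give no event rates, so any count needs assumptions. Let p be the Day 29 incidence and f the hazard after Day 29 relative to before, both assumed. Then

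Day 90 incidence = 1 - (1 - p)^(1 + f × 61/29).

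With p = 20% and about 50 subjects per arm (100 randomized 1:1):

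- f = 0.10: 23.7%, a gap of 3.7 points or about 2 subjects
- f = 0.25: 28.9%, a gap of 8.9 points or about 4 subjects
- f = 1: 50.0%, a gap of 30.0 points or 15 subjects

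Over p from 10% to 70% and f from 0.1 to 1, the values tried gave gaps from 2 to 38 points. A range that wide shows only that the Day 29 and Day 90 rates need not be close. It is not an estimate for this trial.

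**The case against.** The best defence is that the correct periods are already in the SAP. Section 2.2.4 states them, the protocol repeats them, and the sentence in 7.2.5 can be read as describing the pool of events to be coded, without overriding the endpoints. A careful programmer could apply 2.2.4. That is fair, and it makes this a correctable inconsistency and not a lost endpoint. But 7.2.5 is the table specification. It states a different, single period and does not refer back to 2.2.4. Double programming (SAP 4.1) checks that two outputs agree, not which SAP section governs.

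Three stronger readings are tempting, and the documents do not support them:

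- **Late SAEs and deaths will be lost.** This requires the Day 29 statement, which SAP 3.1 confines to disposition and completion. Even then only the summary tables would omit them: SAP 7.2.5 lists every AE and SAE with onset day, seriousness and outcome, and vital status is collected at Days 60 and 90. The Day 29 mortality endpoint in SAP 6.1 does not use the AE tables.
- **68% of the SAE information is at risk.** The figure counts days. Nothing in the documents says how events fall across them.
- **The Day 90 reading mixes clinic data with phone recall.** Collection does become sparser after Day 29, with two phone checks in place of daily in-hospital follow-up. But protocol 4.2 and 7.2.7 also allow Day 15 and Day 29 information, including SAEs and TEAEs, to be taken by phone when a visit cannot be held, so the contrast is not clean.

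The descriptive status of safety (SAP 7) also stands: no alpha, power or efficacy result is touched.

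**Conclusion.** The inconsistency is real. Followed literally, SAP 7.2.5 leaves at least one named safety endpoint tabulated over a period other than its own. On the more natural reading these are the two Day 29 endpoints, whose tables would include Day 30-90 events; on the weaker reading it is the Day 90 SAE endpoint. The documents do not settle which applies, and the number of events involved cannot be derived from them.

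The consequence is limited to descriptive incidence tables, and the listings allow any count to be redone. The change is worth making before the final analysis because it is cheap and these tables carry the safety result. The conclusion rests on the SAP text available for review, from which some pages were removed; the text that remains contains no table-specific AE period.

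**What to change.** In SAP 7.2.5, replace the end-of-study limit with the periods in 2.2.4:

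- **Tables ii-vii** (TEAEs, ADRs, relationship, severity, Grade 3 or higher): onset from randomization through Day 29.
- **Tables viii and ix** (SAEs, potentially related SAEs): onset from randomization through the Day 90 Phone Check.
- **Table i:** two labelled blocks, one through Day 29 and one through Day 90. Filtering its rows one by one would not work: an SAE row to Day 90 could exceed the any-TEAE row to Day 29, and a death row to Day 90 could exceed the Grade 3 or higher row to Day 29. Within a block the rows stay nested.
- **Tables x and xi** (death, withdrawal): state the period, since neither matches a listed endpoint. Death is a seriousness criterion in protocol 8.3.7, so fatal TEAEs are SAEs and Day 90 is consistent for x.

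In the same edit, align the lower bound: 7.2.5 counts events after randomization, while 7.2.1 includes the day of randomization. Day 30-90 non-serious events need no new output, because the existing listing covers them.

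The cost is a few sentences in the SAP, a date filter per table and one extra block in table i. No new data and no protocol change are needed.
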